24.6 Secondary outcomes

For diagnostic accuracy of the first test taken, proportions of observed true positives, true negatives, false positives and false negatives will be presented. Estimates of sensitivity, specificity, positive and negative predictive values will be generated, as well as the positive and negative likelihood ratios together with corresponding 95% confidence intervals, using the Wilson method. Diagnostic accuracy will be calculated for rejection events diagnosed by both methods (biopsy and clinical) for the entire trial period. A sensitivity analysis will include data for the first three months of patient follow up (to which point all suspected rejections are diagnosed using biopsy). Skin flap rejection events, by severity, will be summarised descriptively. Time to first skin flap rejection, transplanted lung and patient survival will be analysed following the methods used for the primary outcome. Competing risks will be considered if the number of deaths not related to the transplanted organ is sufficiently high to warrant such analyses. Transplant lung function (vital capacity, forced expiratory volume) will be analysed using mixed-effects linear regression models, including treatment, and adjusted for centre as a random effect. Development of de-novo specific antibodies, development of graft versus host disease, and evidence of chronic rejection, will be analysed using a mixed-effects logistic regression model, including treatment, and adjusted for centre as a random effect. Safety events (AEs, SAEs, complications), immunosuppressive levels (and requirements) and immunological markers will be summarised descriptively. HRQoL outcomes will be analysed using mixed-effects linear regression model, including treatment and adjusted centre and patient as random effects. Supplementary analyses of HRQoL will also use the area under the curve statistics.

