A series of intestinal transplant patients co-transplanted with a skin flap (n=34; 24 AWT; 10 forearm SSF) were compared to a contemporary cohort of intestinal transplant patients without skin (n=19). The incidence of intestinal transplant rejection of 77% in the first year dropped to 22% when skin was co-transplanted (p<0.01). (Figure 3). Not only did the combined co-transplantation of skin flap and intestine have some immune-modulatory effect, but the sensitivity and visibility of the skin to rejection meant that when rejection was detected in the intestine, it was less severe than in the cohort without the SSF (unpublished data).

[figure not shown]

Figure 3. Kaplan Meier time to first rejection event (rejection free survival)

The ability of the SSF to diagnose rejection in the intestine transplant was found to have a sensitivity of 94%, specificity 89%, NPV 98%, PPV 44%, if assessed at time of test taken. We also saw that when the skin flap initially reported false positive (skin flap positive for rejection but the initial intestinal biopsy was negative for rejection) in seven out of nineteen events, the transplanted intestine biopsies became positive for rejection two to ten days later after repeated biopsy (despite treatment). This demonstrates that the skin changes indicating rejection were seen before the intestinal rejection changes occurred. This provides further evidence that the skin flap was useful for early detection of rejection before the intestine was affected. It is presumed that in the other twelve of nineteen events, treatment of the skin rejection prevented rejection appearing in the intestine. On the four occasions in which the intestinal biopsy signalled rejection before the skin biopsy, three had no skin biopsy taken at the time, and one had non-specific features.

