15.3 Randomisation methodology

Consenting participants will be allocated randomly (1:1) to either lung transplant with SSF transplant or lung transplant only.

Allocations will be generated using permuted block randomisation, with varying block sizes, stratifying for recruiting centre.

The randomisation schedule(s) will be designed by the OCTRU study statistician and full details will be detailed in a study randomisation and blinding plan.

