16.8 Detecting, diagnosing and managing rejection

If any events occur that suggest lung transplant rejection, such as a clinically significant drop in forced expiratory volume in 1 second (FEV1) of >10% or new symptoms of lung failure, then the usual sequence of clinical investigations will be performed and may include a tissue biopsy. The decision to perform a biopsy will be made in accordance with local site practice.

If a lung biopsy is performed, a skin biopsy will also be taken by the local health team for any participants with a SSF. The biopsy samples taken (lung and/or skin) will be examined by the local pathology team. Remaining samples embedded in paraffin blocks will be sent to the University of Oxford for the mechanistic studies at the completion of the 12 month follow up period;

If signs of skin rejection occur, the participant will either be examined in person by a study clinician (e.g. during a routine or extra visit) or they will be asked to send a photo of their skin flap to the research team/local healthcare transplant teams. The sending of any photographs from a participant to the research team or between local healthcare team and the research team will be done in accordance with local site practice for remote consultations; photographs will be stored within the participant's medical notes.

Consensus determination of rejection change in the skin will trigger an outpatient visit. Clinical features of the rash, investigations such as blood tests, sputum or bronchial brushings/, bronchoalveolar lavage if available, and lung function assessment and skin and/or lung biopsies (if taken) will be analysed for rejection.

All investigations for rejection will be performed at the discretion of the participating site/clinician and considered part of standard of care. This does not include the protocol skin biopsies taken at 3, 6 and 12 months which are required for the purpose of the study only.

A summary of the biopsy requirements for suspected rejection is provided in Table 2.

Table 2: Biopsy requirements/investigations for suspected rejection events

	Lung biopsy	Skin biopsy required (sentinel skin flap recipients only)
Signs/symptoms of lung rejection WITHOUT visible skin changes/rash only	In accordance with local policy*	Yes
Signs/symptoms of lung rejection WITH visible skin changes/rash only	In accordance with local policy*	Yes
Visible skin changes/rash	In accordance with local policy if signs of lung rejection present	Yes

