16.10 Treatment of rejection

Acute rejection of the lung will be detected and treated according to established practice at the participating transplant centre. If rejection in either skin or lung is confirmed by clinical findings or pathology (BANFF grade>1 skin and ISHLT grade A>1 for lung) this will be recorded. Decision on instituting treatment will be at the discretion of the local care team. Treatment given, treatment date and outcome of treatment for rejection will be recorded. Normal local transplant follow-up protocols will continue with the addition that the skin flap will also be biopsied whenever the lung is biopsied.

The usual treatment of biopsy proven acute rejection of the SSF for Banff Grade 1 rejection will be a single 500mg dose of intravenous methylprednisolone with correction or escalation of daily immunosuppression if required, and for Banff Grade 2-4 rejection, is 3 daily doses of 500mg intravenous methylprednisolone with escalation of daily immunosuppression if required. However, any such treatment is at the determination of the clinical relevance by the local transplant team.

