24.2 Sample Size/Power calculations

The anticipated 12-month rejection rates for lungs in the control arm by 12 months is 80%. Published rates vary between 33-100% (43–46) depending on definition and grade of rejection and method of analysis. However, a comprehensive study of regular transbronchial biopsies in 299 lung transplant patients showed a cumulative incidence of rejection (≥grade A1) of 91.7% in the first 12 months and (≥grade A2) of 77.9% (46).

In the SSF intestinal study, we observed a 72% reduction in biopsy-proven acute rejections from the 77% rejection rate in the control arm reducing to 22% in the with skin arm. However, as a more conservative estimate for this study, we consider a relative reduction of a third from 80% to 53.33% (corresponding to an absolute difference of 26.67%) to be clinically meaningful. 128 participants who have had a transplant are required for the analysis to achieve 90% power at a two-sided significance level of 5%. To allow for a 15% loss to follow-up or death by 12 months (76 per trial arm) 152 participants need to have been randomised and transplanted. In total, approximately 254 randomisations will be required to achieve this number and account for participants not proceeding with transplant.

Assessment of the diagnostic accuracy of the SSF compared to the current reference standard (organ biopsy) is a secondary objective of this study, and is undertaken in participants who received an SSF. Assuming approximately 80% specificity, and 90% specificity, based on previous studies, 95% confidence intervals (Wilson method) around the sensitivity, specificity, positive and negative predicted values will have a width of approximately 20-30%, depending on the observed sensitivity, specificity and event rates. A sample size of 64 participants receiving SSF and providing one-year follow-up data, an expected rejection rate of 53%, and anticipated values of 80% and 90% for sensitivity and specificity, respectively, will provide approximately 80% power (at a one-sided 5% significance level) to show that the observed sensitivity and specificity in the study are statistically significantly higher than 60% and 70%, respectively.

Since the proposed mechanistic sub-studies are intended to be hypothesis generating, no formal sample size calculations have been performed.

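### The flap's accuracy table has no rule for flap-positive participants who are treated, so a lung rejection averted by acting on the flap is scored as a false positive

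*Protocol*

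**What the plan says.** Diagnostic accuracy of the flap is the first secondary outcome (Protocol 9.3), assessed in flap recipients only. The data listed for it are the date of first diagnosed lung rejection and the date and method of first diagnosed skin rejection. The reference standard is lung biopsy and/or clinical diagnosis.

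Section 24.6 builds the counts of true and false positives and negatives on the first test taken and adds that "Diagnostic accuracy will be calculated for rejection events diagnosed by both methods (biopsy and clinical) for the entire trial period". A sensitivity analysis uses the first three months. No pairing window is given, and nothing is said about treatment between the skin result and the lung result.

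On what follows a positive flap, 16.10 names methylprednisolone and says: "usual treatment of biopsy proven acute rejection of the SSF for Banff Grade 1 rejection will be a single 500mg dose". Higher grades get a longer course, and all of this is subject to the local team's judgement of clinical relevance. In Table 2 of 16.8, the lung-biopsy entry for visible skin changes alone is "In accordance with local policy if signs of lung rejection present". The visit triggered by a rash does include lung function assessment.

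The background (8.3) reports 19 events in the intestinal series that were skin-positive with an initially negative intestinal biopsy. Seven turned positive two to ten days later. For the other twelve the protocol presumes that "treatment of the skin rejection prevented rejection appearing in the intestine".

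Section 24.2 claims about 80% power, one-sided 5%, to show sensitivity above 60% and specificity above 70% with 64 flap recipients and a 53% rejection rate.

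**The concern.** The index test prompts a treatment that is meant to stop the reference-standard event from happening. The lay summary states this as the purpose: treat on the rash so that the organ does not reject. An accuracy table that ignores the treatment has only one place for a participant who was flap-positive, treated and never recorded with lung rejection, namely the false-positive cell. The better the flap works by prompting early treatment, the worse its specificity and positive predictive value (PPV) look.

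The missing time link adds an error of the opposite kind. A lung rejection early in the year and an unrelated skin rejection late in the year can be matched as a true positive, which flatters sensitivity and PPV. The net direction for PPV is therefore not known, and the reported figures would be hard to interpret either way. Section 24.4 also has the DSMC review diagnostic accuracy at interim, so the same difficulty arises before the final report.

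**Working it through.** **Inputs (Protocol 24.2).** The effect is "a relative reduction of a third from 80% to 53.33" per cent; 64 flap recipients provide one-year data (half of the 128 analysed); anticipated sensitivity is 80% and specificity 90%; the benchmarks are 60% and 70%, one-sided 5%.

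**The plan's figure reproduced.** Expected with lung rejection: 64 × 0.5333 = 34.1. Without: 64 − 34.1 = 29.9.
- Sensitivity 80% against 60%, n = 34: exact binomial power 77.3%, normal approximation 81.6%.
- Specificity 90% against 70%, n = 30: success needs at least 26 of 30; exact power 82.5%, normal approximation 87.3%.

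About 80% is confirmed. The reconstruction also shows the unit being counted: 53% is the 12-month rejection rate, so the specificity denominator is participants with no lung rejection during the year.

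**Effect of treatment-averted rejections.** Prevented rejections under the planned effect: 64 × (0.80 − 0.5333) = 17.1. All of them lie among the 29.9 participants without rejection. Let q be the share prevented by treating a positive flap. Each such participant is flap-positive and lung-negative. Assume specificity of 90% in the rest. Then

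specificity = 0.9 × (29.9 − 17.1q) / 29.9

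PPV = 27.3 / (27.3 + false positives), where 27.3 = 0.8 × 34.1.

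| q | Averted via flap | False positives | Specificity | PPV | Exact power, specificity >70% (n=30) |
|---|---|---|---|---|---|
| 0 | 0 | 3.0 | 90% | 90% | 82% |
| 0.10 | 1.7 | 4.5 | 85% | 86% | 52% |
| 0.25 | 4.3 | 6.8 | 77% | 80% | 15% |
| 0.50 | 8.5 | 10.7 | 64% | 72% | <1% |
| 1.00 | 17.1 | 18.3 | 39% | 60% | about 0% |

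Expected specificity reaches 70% when 1 − 17.1q/29.9 = 0.7/0.9, that is q = 0.39, or between six and seven participants.

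**The intestinal series (8.3).** With PPV 44% and 19 false positives, true positives = 19 × 0.44/0.56 = 14.9, about 15. With sensitivity 94% and specificity 89%, false negatives are about 1 and true negatives 19 × 0.89/0.11 = 153.7, about 154. As scored, PPV = 15/34 = 44%. Counting the seven later positives as true gives 22/34 = 65%. Setting the other twelve aside as well gives 22/22 = 100%. The classification rule drives the result.

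**The case against.** Several stronger readings are tempting, and the documents do not support them.

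- *Every averted rejection becomes a false positive.* No. Prevention by immune modulation without a positive flap, a mechanism the protocol also proposes, creates none. A treated participant whose lung rejects later in the year can score as a true positive. The false-positive scoring follows from the two-by-two layout; 24.6 does not spell it out.
- *Steroid is given before the lung is verified.* This is not a rule of the protocol. Treatment is discretionary, lung function is assessed at the rash visit, a lung biopsy may be taken, and clinical diagnosis counts as reference. The text shows only that a lung biopsy is not required.
- *Scoring over the whole year is the cause.* It is not. The 19 events in 8.3 arose with accuracy assessed at the time of the test. For the same reason the three-month sensitivity analysis does not remove the problem.
- *The flap could fail a 70% specificity test.* The 70% is a power benchmark in 24.2; 24.6 plans estimates with Wilson intervals and names no decision rule.

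The size also rests on an unknown q. In the intestinal series specificity was still 89% with flap rejection treated, although that series appears to be counted per test, with about 154 true negatives, and so is not directly comparable. Section 8.4 reports flap rejection below 25% alongside a solid organ transplant, whereas q = 0.39 implies about 57% flap-positive: (27.3 + 9.0)/64. That argues against the upper end of the table. It cannot fix q, since the planning figures already imply 47% at q = 0: (27.3 + 3.0)/64.

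Finally, the phrase about the first test taken might be read as limiting the pairing, and a window could be left to the SAP. But 24.6 sets its own table and period, and 24.2 counts by 12-month status. What the protocol states leads to the problem, so this is more than missing detail.

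**Conclusion.** The point holds in a limited form. As 24.6 stands, a flap-positive participant who is treated and has no recorded lung rejection is scored as a false positive even where treatment averted the rejection, and skin and lung events far apart in time can be matched. Specificity and PPV cannot then be read as properties of the flap, and the stated power for specificity makes no allowance for this. On the planning figures, apparent specificity is 90% at q = 0, 77% at q = 0.25 and 64% at q = 0.5. This assumes that the planned effect is realised, that specificity is 90% in the other lung-negative participants, and that each flap-averted case is scored skin-positive and lung-negative. No document gives q, so these figures illustrate the range and are not predictions.

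A reader might infer that the primary result is compromised. It is not: lung rejection is compared between arms without reference to the flap result. No view is taken on the treatment or biopsy rules.

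**What to change.** In 24.6, make the main accuracy table episode-paired: each flap test against lung status, by biopsy or clinical diagnosis, within a fixed window around the test that is stated in advance.

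Report as a separate group all flap-positive episodes that were treated without lung rejection being diagnosed in the window. The group must include both those with no lung assessment and those that were lung-negative at the test and then treated. Setting aside only the former would still score the 8.3 events as false positives, because they had a negative initial biopsy.

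Give sensitivity, specificity, PPV and negative predictive value three ways: group excluded, all counted as true positive, all counted as false positive. None of the three is the answer alone. In the intestinal series, if all 19 events were treated and the window covered ten days, PPV would be 100% (22/22), 100% (34/34) and 65% (22/34).

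Keep the whole-period table as secondary. State in 24.2 that the specificity power assumes no treatment-averted rejections.

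The cost is wording and a little more analysis. Biopsy results, treatment and treatment dates are already recorded (16.10, 17.3), and no clinical procedure changes. There will be fewer evaluable pairs and wider intervals, and if a participant contributes more than one episode the interval method must allow for the repetition.

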10.6 Central review procedures

Not applicable. There are no central review procedures for this study. Where site staff require a second expert opinion of the assessment of the skin rash this will be sought as described in section 16.8 Detecting, diagnosing and managing rejection.

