*sites will take lung biopsies in accordance with local site practice; clinical diagnosis of lung rejection may be used in place of biopsy-confirmed rejection where this is also local site practice.

18.2 Sample handling for standard of care samples and trial-specific samples to be analysed in local Trust's laboratories

Standard of care samples and trial-specific samples to be analysed in local Trust laboratories will be taken and processed by laboratories in accordance with local site practice. This includes labelling of samples with standard patient identifiers. Results will be reported back in the usual way according to local practice and accessed by the site research team, and entered into the study database.

Sample Type	Time point	Test(s) to be undertaken on the sample
Lung biopsy	Upon suspicion of rejection, and when taken for monitoring as standard of care	Biopsy will be analysed by local pathology laboratory for signs of rejection. Results will be reported back on histopathology report.
Skin biopsy	Upon suspicion of rejection, and at baseline, 3, 6 and 12 months.	Biopsy will be analysed by local pathology laboratory for signs of rejection. Results will be reported back on histopathology report.

Other samples required for routine clinical follow-up following transplantation will be taken and processed by local Trust laboratories as required e.g. blood samples, broncho-alveolar samples, sputum samples.

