24.5 Primary outcome

The primary outcome of the study is absolute difference in rejection rates (clinical or biopsy) at 12 months post randomisation. The absolute risk difference, and corresponding 95% CIs, will be obtained from a mixed-effects Cox proportional hazards models, including treatment and adjusted for centre as a random effect, analysing time to first lung rejection (43). If the proportional hazards assumption is not met, alternative parametric methods will be considered. The treatment groups will also be compared using Kaplan-Meier curves and log rank tests. Events, by severity, will be summarised descriptively. Sensitivity analyses for the primary outcome will include alternative definitions of the primary endpoint, including lung rejections of ISHLT grade 2 or higher, and ISHLT grade 3 or higher. The primary analysis will

be repeated for the per-protocol population, excluding participants with major deviations from the study protocol.

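### Section 24.6 assumes every suspected rejection to three months is biopsied, against 15.4, 16.8 and 18.1, and no named between-arm analysis is limited to biopsy-proven lung rejection at grade A≥1

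*Protocol*

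**What the plan says.** **Diagnostic accuracy (9.3, 24.6).** The flap is compared with a reference standard of lung biopsy and/or clinical diagnosis, in the intervention arm only. The main analysis uses both: "Diagnostic accuracy will be calculated for rejection events diagnosed by both methods (biopsy and clinical) for the entire trial period". A sensitivity analysis keeps only the first three months, on the ground that this is the period "to which point all suspected rejections are diagnosed using biopsy".

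**How lung rejection is diagnosed (16.8, 18.1).** When rejection is suspected, "then the usual sequence of clinical investigations will be performed and may include a tissue biopsy". Section 16.8 adds: "The decision to perform a biopsy will be made in accordance with local site practice". The footnote to Table 4 in 18.1 states that "clinical diagnosis of lung rejection may be used in place of biopsy-confirmed rejection where this is also local site practice".

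**Role of the flap in the work-up (16.8).** "Consensus determination of rejection change in the skin will trigger an outpatient visit". At that visit the appearance of the rash is weighed together with lung function, laboratory tests and any biopsies.

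**Blinding and review (15.7, 10.6).** Site staff are not blinded. On adjudication, 10.6 says: "There are no central review procedures for this study".

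**Primary outcome (synopsis, 24.5, 24.8).** The endpoint is lung rejection by clinical criteria and/or biopsy at ISHLT A≥1. The named alternative definitions in 24.5 are described as "including lung rejections of ISHLT grade 2 or higher, and ISHLT grade 3 or higher". Section 24.8 adds a composite of lung rejection at ISHLT A grade 1 or above, graft failure defined by a BANFF grade, and death.

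**The concern.** There are two linked but separate problems.

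First, the three-month analysis is useful only if its premise is true. Its purpose is to test the flap against histology, free of clinical judgement. If some early rejections are diagnosed clinically, by staff who have seen or been told about the flap, the index test can influence the reference standard. Agreement between the two may then be overstated, and the analysis would be reported as biopsy-verified when it is not.

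Second, the same kind of diagnosis counts in the primary endpoint, where only one arm has a flap to look at. A rash can prompt extra lung work-up, and a normal flap can make a clinician less ready to label a decline as rejection. An obvious check is to repeat the comparison on histologically proven events at the endpoint's own threshold, and the protocol does not name that analysis.

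**Working it through.** **1. Is the premise in 24.6 supported elsewhere in the protocol?**

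| Section | Content on lung biopsy | Exception for months 0–3? |
|---|---|---|
| 24.6 | Every suspected rejection to three months is biopsied | This is the claim |
| 16.8, text | Biopsy is optional; the site decides | None |
| 16.8, Table 2 | Lung biopsy by local policy with or without a rash; for a rash alone, only if there are also lung signs | None |
| 17.1, Table 3 | Lung biopsy only if routine at that centre | None |
| 18.1, Table 4 and footnote | Biopsy on suspicion only where that is local practice; clinical diagnosis otherwise allowed | None |
| 15.4 | Centres differ in whether they assess rejection clinically or by biopsy; this is the reason for stratifying | None |
| 8.1 | Only some centres do surveillance biopsies | None |

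No section supports the statement and several point against it. A three-month cut-off therefore does not guarantee a biopsy reference.

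**2. Does any named between-arm analysis use biopsy-proven A≥1?**

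- 24.5, grades ≥2 and ≥3: these rest on a histological grade, but they drop A1 events, which the endpoint counts. The protocol does not say how an ungraded clinical diagnosis is treated in them.
- 24.8, composite: the lung component is at A≥1, but death and a BANFF-graded component are added. BANFF is the protocol's skin grade (9.3, 16.10), so as written that component can arise only in patients with a flap.
- 24.5, per-protocol analysis: same endpoint, fewer patients.

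None is limited to biopsy-proven lung rejection at A≥1.

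**3. How much does the grade ≥2 analysis leave out?** Section 24.2 cites a transbronchial biopsy series with 12-month cumulative incidence of 91.7% at A≥1 and 77.9% at A≥2.

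- Reached A1 but not A2: 91.7 − 77.9 = 13.8 points.
- As a share of all patients with rejection: 13.8 / 91.7 = 15%.

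If the trial resembles that series, about one patient in seven with biopsy-proven rejection would not count at grade ≥2.

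**4. The planned effect, for scale.** The sample size reproduces and is not in dispute. With p1 = 0.80, p2 = 0.5333, mean 0.6667, two-sided 5% and 90% power:

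n per arm = [1.960 × √(2 × 0.6667 × 0.3333) + 1.2816 × √(0.80 × 0.20 + 0.5333 × 0.4667)]² / 0.2667² = (1.307 + 0.819)² / 0.0711 = 63.6, so 64 per arm and 128 in total. Then 64 / 0.85 = 75.3, so 76 per arm and 152 in total.

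The target difference is 26.67 points. The protocol gives no share of rejections diagnosed without biopsy, so no bias can be derived to set against it.

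**5. Can an analysis based on actual biopsies be done?** Yes. The rejection-event form in 17.3 records the method of diagnosis, the reason for suspicion and the biopsy results. Section 16.8 requires a skin biopsy whenever the lung of a flap recipient is biopsied, so pairs will exist. The limit is Table 2: a rash without lung signs leads to no lung biopsy, so some flap-positive episodes will never be verified.

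**The case against.** **The statement in 24.6 may simply describe what the centres do early on.** It may, since local practice could be to biopsy every early suspicion. No section says so, and 15.4 and 8.1 suggest otherwise. What stands is that this calls for reconciliation and is not proof that early biopsies will be missing.

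**A further sensitivity definition belongs in the SAP.** This is partly right. The list in 24.5 is not worded as exhaustive, and the SAP could add a biopsy-proven A≥1 analysis. The second half of the point is therefore a recommendation to name it now. The first half is different, because 24.6 states as fact something other sections contradict.

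**The mechanism is only a possibility.** This stands. Under Table 2, suspected lung rejection leads to biopsy by local policy whether or not there is a rash, and no rule lets a normal flap exclude rejection. Influence of the flap on clinical diagnosis is a risk left open, not something the protocol shows will happen.

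**Stronger readings the documents do not support.**

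- A reader might infer that the three-month analysis is the only one based on histology. It is not: 24.5 and 24.8 contain ISHLT-graded analyses.
- A reader might infer that its weak premise leaves the trial unable to tell a flap effect from an ascertainment effect. That does not follow. The analysis covers the flap arm alone and could not compare arms even if every episode were biopsied.
- A reader might attach a number to the bias. Suppose half of an 80% rejection rate is diagnosed clinically, and 10% to 33% of those diagnoses are not made in the flap arm. The spurious difference is then 0.80 × 0.5 × 0.10 = 4 points to 0.80 × 0.5 × 0.33 = 13 points. Neither share is in the protocol, and rash-triggered work-up would push the other way. This shows scale under assumptions and is not evidence of bias.

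**Conclusion.** The point holds in two parts.

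1. Section 24.6 conflicts with 15.4, 16.8 and 18.1. Run as written, the three-month accuracy analysis is not assured the biopsy reference it claims, and it may include clinical diagnoses made by unblinded staff with sight of the flap.
2. The primary endpoint counts the same kind of diagnosis with no central review, and no named between-arm analysis is confined to biopsy-proven lung rejection at A≥1.

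The direction and size of any bias are unknown, because the clinical-only share is not given and the two possible influences of the flap oppose each other. The one figure available from the protocol is that a grade ≥2 analysis would omit about 15% of patients with rejection, assuming the cited series is a fair guide. The matter should be corrected before analysis. It does not undermine the design or the sample size.

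**What to change.** **Section 24.6.** Reconcile the parenthesis with 16.8 and 18.1. Define the biopsy-verified accuracy analysis by episodes in which lung status was established by lung biopsy, at any time in follow-up, instead of by the first three months. State how this fits the rule that the first test taken is analysed. Report the number of flap-positive episodes without a lung biopsy, and note that leaving them out can overstate specificity (partial verification).

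**Section 24.5.** Add a between-arm sensitivity analysis, by the primary method, counting only biopsy-proven ISHLT A≥1 lung rejection, identified from the method of diagnosis on the rejection form. Say how a clinical-only diagnosis is handled there and in the grade ≥2 and ≥3 analyses: whether the participant stays at risk or is censored.

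**Cost.** Protocol or SAP wording only, with no new data and no change to biopsy practice. There will be fewer events and wider intervals, and centres that rely on clinical diagnosis will contribute little. The decision to biopsy remains unblinded, so the new analysis reduces the problem without removing it.

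**Two remedies to avoid.** Excluding lung events first suspected because of the skin would remove true rejections from the flap arm only, which favours the flap. Redefining clinical diagnosis within the primary endpoint would change the primary outcome and what sites must apply, and this point does not need it.
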